8.2.1.3 Follow-Up Period

The follow-up period will include 2 visits, one scheduled 3 days after the last IMP dose and one scheduled 30 days after the last IMP dose.

8.2.1.3.1 FU-V1 (3 days after the last IMP dose)

At FU-V1 the following activities and assessments will be performed:

- Assessment of changes in the medical history
- Physical examination
- Vital signs, including blood pressure, pulse rate and body temperature
- Laboratory safety assessments, including hematology, biochemistry, and urinalysis
- ECG
- · Concomitant medications
- AEs

8.2.1.3.2 FU-V2 (30 days after the last IMP dose)

At FU-V2 the following activities and assessments will be performed:

- Assessment of changes in the medical history
- Physical examination
- Vital signs, including blood pressure, pulse rate and body temperature
- Laboratory safety assessments, including hematology, biochemistry and urinalysis
- ECG
- Concomitant medications
- AEs

Date: 13 December 2023

Sponsor: Atlas Molecular Pharma S.L.

Study Code: ATL001-PI-CEP NCT No.: 05647343

8.3 Discussion of Study Design, Including the Choice of Control Groups

This is a Phase I, double-blind, randomized, parallel-design, placebo-controlled study with a dose escalation design. It will be performed in healthy subjects who will receive treatment with oral ATL-001 or placebo once daily for 5 days. Healthy subjects were chosen for this study to avoid confounding factors from the disease or concomitant drugs in subjects with CEP that may hinder the evaluation of safety. Additionally, ethical considerations dictate exploration of safety and tolerability in healthy subjects first as subjects with CEP may be more vulnerable to side effects caused by the compound. Full details on study design are presented in Section 8.1.

ATL-001 is a new oral formulation of ciclopirox olamine, including alginate and tocofersolan, currently under development for the treatment of subjects with CEP. This new oral formulation was developed to improve the local tolerance of ciclopirox olamine, which otherwise induces dose-dependent gastrointestinal toxicity. ATL-001 has been studied *in vitro* and *in vivo*, and its safety profile has been found to be acceptable for initiating this trial. For information on ATL-001 non-clinical pharmacology, PK and toxicology as well as relevant disease background information, please refer to Section 6.2 and to the Investigator's Brochure.

The assessment of the expected benefits and risks of the current Phase I study is based on the study design and risk-minimization measures as well as the safety profile in pre-clinical studies, including toxicology assessments, and on predictions of the activity of ATL-001 in the subjects as derived from the comprehensive pre-clinical pharmacological data package.

The Sponsor has designed the study in such a way that the safety of ATL-001 can be investigated while keeping potential risks for the subjects to a minimum (see Section 6.5). Further, the dose escalation design ensures that the next dose cohort only will only occur after the safety and tolerability data from the prior cohort is reviewed and deemed acceptable.

The study is placebo controlled to provide a comparison group and to account for the placebo effect.

8.4 Study Period

The anticipated study duration is about 11 months, with up to 66 days duration per subject.

For each cohort, after a 30-day Screening period to establish subjects' eligibility, the subjects will be treated for 5 days (the treatment period) and followed by 30 days of observation and assessment of treatment outcomes (the follow-up period).

8.5 End of Study

The end of study is defined as the date of the last subject's last visit. The study will be completed after the last subject has performed the safety follow-up 30 days after the last IMP administration (FU-V2).

The Sponsor may discontinue the complete study at any time, for ethical or scientific reasons. The PI is entitled at any time to stop the study due to medical reasons. In such a case, the PI should consult the Sponsor at the earliest opportunity.

Version: 4.0 Date: 13 December 2023 Sponsor: Atlas Molecular Pharma S.L. Study Code: ATL001-PI-CEP

NCT No.: 05647343

9. SELECTION OF STUDY POPULATION

9.1 Number of Subjects

The study will consist of five sequentially recruited cohorts of 8 subjects each, resulting in up to 40 randomized subjects. Sample size considerations are detailed in Section 13.2.

9.2 Inclusion Criteria

The subjects have to meet all of the following criteria to be eligible to enter the study:

- 1) Healthy male or female subjects 18 to 65 years of age, inclusive
- 2) Body mass index (BMI) within the range of 18.0 to 33.0 kg/m², inclusive, and a minimum weight of at least 50.0 kg and maximum weight of 100.0 kg at Screening
- 3) Estimated Glomerular Filtration Rate (eGFR) > 90 mL/min/1.73 m² at Screening
- 4) Female subjects of childbearing potential must be using and willing to continue using two medically acceptable contraceptive precautions from Screening and for at least 1 month after the last study drug administration. Medically acceptable forms of contraception include sexual abstinence [periodic abstinence (e.g., calendar, ovulation, symptothermal and post-ovulation methods) are not acceptable], combined (oestrogen and progestogen containing) hormonal contraception associated with inhibition of ovulation (oral, intravaginal or transdermal), intrauterine devices (IUD), intrauterine hormone-releasing systems, and bilateral tubal ligation for subjects
- 5) Female subjects of non-childbearing potential must be amenorrhoeic for at least 2 years or had a hysterectomy and/or bilateral oophorectomy/salpingo-oophorectomy (as determined by subject medical history)
- 6) Male subjects of reproductive potential with a partner(s) of childbearing potential, must be using and willing to continue using two medically acceptable contraceptive precautions from Screening and for at least 1 month after the last study drug administration. Medically acceptable forms of contraception include abstinence, vasectomy, or male condom for subjects
- 7) Female subjects must have a negative pregnancy test
- 8) Must understand and provide written informed consent prior to the initiation of any protocol-specific procedures
- 9) Must be willing and able to abide by all study requirements and restrictions

9.3 Exclusion Criteria

Subjects meeting any of the following criteria will not be permitted to enter the study:

- 1) Current drug or alcohol dependence (excluding caffeine), based on self-report, including subjects who have been in a drug rehabilitation program
- 2) Current smoker or a history of using tobacco products within 3 months prior to Screening
- 3) Clinically significant abnormalities on physical examination, medical history, 12-lead ECG (i.e., QTc > 440 ms for male subjects and > 450 ms for female subjects), vital signs, or laboratory values, as judged by the investigator or designee
- 4) History or presence of any clinically significant illness (e.g., cardiovascular, pulmonary, hepatic, renal, hematologic, gastrointestinal, endocrine, immunologic, dermatologic, neurologic, oncologic, musculoskeletal, or psychiatric) or any other condition, which in the opinion of the investigator would jeopardize the safety of the subject or the validity of the study results
- 5) Use of a non-prescription drug within 14 days prior to the first drug administration. Subjects who have taken over-the-counter medication may still be entered into the study, if in the opinion of the investigator or designee, the medication received will not interfere with the study procedures or data integrity or compromise the safety of the subject
- 6) Use of any prescription medications, recreational drugs, or natural health products (except vitamin or mineral supplements, acceptable forms of birth control, and hormone replacement) within 14 days prior to first drug administration or throughout the study, unless in the opinion of the

Version: 4.0

Date: 13 December 2023

Sponsor: Atlas Molecular Pharma S.L. Study Code: ATL001-PI-CEP

NCT No.: 05647343

investigator or designee, the product will not interfere with the study procedures or data integrity or compromise the safety of the subject

- 7) Use of any medication that interfere with the glucuronidation metabolic pathway within 14 days prior to first drug administration
- 8) Positive urine drug screen
- 9) Positive breath alcohol test. If a subject presents with positive breath alcohol test, the subject may be rescheduled at the discretion of the investigator or designee
- 10) Female subjects who are currently pregnant or lactating or who are planning to become pregnant within 60 days of last study drug administration
- 11) Known history of allergy or hypersensitivity to any component of the active drug or placebo
- 12) Positive for Hepatitis B, Hepatitis C, HIV or COVID-19
- 13) Treatment with any investigational drug within 30 days prior to first drug administration in the treatment phase
- 14) A subject who, in the opinion of the investigator or designee, is not considered to be suitable and is unlikely to comply with the study protocol for any reason

9.4 Discontinuation/ Withdrawal Criteria

9.4.1 Withdrawal from the Study

Subjects are free to discontinue their participation in the study at any time without having to specify their reasons. Furthermore, subjects may be withdrawn from the study at any time, if deemed appropriate by the Investigator.

Potential reasons for withdrawal of subjects from this study are:

- Refuses to cooperate
- Experiences relevant signs or symptoms affecting subject safety
- Presents hypersensitivity reactions to the IMP
- The decision of a subject to withdraw from the study (including if the subject withdraws informed consent)
- Requires a medication that is prohibited by the protocol (see Section 10.6.2)
- Does not complete the study as outlined in the study protocol
- Is lost to follow-up

The reason and date the subject is withdrawn from the study will be documented in the electronic case report form (eCRF) (e.g., lost to follow-up, consent withdrawn, AEs, etc.). If a subject is withdrawn from the study, the Investigator should attempt to complete all discharge procedures. All AEs should be followed up according to Section 12.

If the subject withdraws consent or he/she is withdrawn from the study, all data collected until the time of withdrawal will be used in the analyses, unless this is prohibited by local regulations. The Investigator must document the withdrawal in the site study records.

In case of a withdrawn subject from the study, he/she may be replaced with another subject at the Sponsor's discretion. The replacement subject will be assigned to the same regimen dosage.

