9.4.2 Withdrawal from Treatment

Subjects may voluntarily discontinue treatment with the IMP for any reason at any time. Subjects may be also withdrawn from the IMP at any time, if deemed necessary by the Investigator.

Potential reasons for withdrawal of subjects from the study treatment are:

 Occurrence of an AE of severe intensity (grade ≥3) which does not justify the continuation of the study treatment, or a SAE that will be judged by the Investigator as at least possibly drug-related

Date: 13 December 2023

Sponsor: Atlas Molecular Pharma S.L. Study Code: ATL001-PI-CEP

NCT No.: 05647343

- Use of non-permitted concomitant medications (see Section 10.6.2)
- The decision of a subject to withdraw from the treatment
- Discontinuation of contraceptives during the treatment period
- Pregnancy

Subjects who discontinue treatment with the IMP should not be considered withdrawn from the study. They should return for follow-up visits. If subjects fail to return for these assessments for unknown reasons, every effort (e.g., telephone, e-mail, and letter) should be made by the Investigator to contact them.

In case of a subject discontinuing the study treatment, he/she may be replaced with another subject, at the Sponsor's discretion. The replacement subject will be assigned to the same regimen dosage.

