10.6.1 Permitted Medications

No concomitant medications will be allowed during the treatment period of the study.

If considered necessary for the subject safety and well-being, concomitant medication may be given at the discretion of the Investigator. However, concomitant medication administered during the study may lead to withdrawal of the subject from the study (see Section 9.4). Decisions regarding replacements of subjects requiring concomitant medications will be discussed with the Sponsor on a case by case basis.

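### Protocol 9.4.1 and 9.4.2 give two routes for the same prohibited-medication trigger, so a dosed subject's FU-V1 and FU-V2 safety panels may, but need not, be lost

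*Protocol*

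**What the plan says.** Protocol 9.4.1 (leaving the study) includes this potential reason: "Requires a medication that is prohibited by the protocol (see Section 10.6.2"). The same list contains "Experiences relevant signs or symptoms affecting subject safety", and hypersensitivity to the IMP. For a subject who leaves by this route, the section says: "If a subject is withdrawn from the study, the Investigator should attempt to complete all discharge procedures". It adds: "All AEs should be followed up according to Section 12". On data use it says that "all data collected until the time of withdrawal will be used in the analyses", subject to local regulations.

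Protocol 9.4.2 (stopping treatment) includes this potential reason: "Use of non-permitted concomitant medications (see Section 10.6.2"). Its list also holds severe AEs (grade 3 or above) that rule out further treatment, and SAEs judged at least possibly related. For subjects on this route it says: "Subjects who discontinue treatment with the IMP should not be considered withdrawn from the study. They should return for follow-up visits".

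Protocol 10.6.1 lets the investigator give medication needed for the subject's safety, but warns that "concomitant medication administered during the study may lead to withdrawal of the subject from the study (see Section 9.4"). Protocol 10.6.2 forbids all concomitant medication during the treatment period.

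**The concern.** One event, taking a medication that 10.6.2 forbids, appears under two headings with different consequences. If the site uses 9.4.2, the subject stays in the study and returns for FU-V1 and FU-V2. If it uses 9.4.1, the protocol does not require either visit.

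This matters because both visits include physical examination, vital signs, laboratory tests and ECG (Protocol 8.2.1.3.1 and 8.2.1.3.2). Clinically relevant changes in those measurements are part of the primary endpoint (Protocol 7). QTcF is a dose-limiting criterion up to FU-V1 (Protocol 8.1.3). Nothing is imputed (Protocol 13.1.2.3), and each cohort has only six active subjects. The people concerned are dosed healthy volunteers with symptoms or a need for medication. Gastrointestinal toxicity is the identified risk (Protocol 6.5), so symptomatic medication during the five dosing days is foreseeable.

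**Working it through.** The plan states no figure on this point. The check is a comparison of sections, followed by a count of scheduled panels.

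**1. Do the two triggers separate?** No. One list speaks of requiring the medication and the other of using it, and both refer to 10.6.2. A subject who needs a drug and takes it meets both.

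**2. Does another section choose the route?** No.
- 10.6.1 names withdrawal from the study but cites 9.4 as a whole. Its case-by-case rule concerns replacement only.
- 10.7 (omitted dose) leaves possible withdrawal to discussion with the sponsor.
- 14.11 gives the sponsor the decision after a major deviation, a class that includes prohibited medication.
- Neither 10.7 nor 14.11 states a criterion, or says whether study or treatment withdrawal is meant.

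**3. What does each route require?**

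| | 9.4.1, leaves study | 9.4.2, stops IMP |
|---|---|---|
| FU-V1 and FU-V2 panels | not required | subject should return |
| At exit | attempt at discharge procedures, not defined | not applicable |
| AE follow-up | kept (Section 12) | kept |
| Use of later panels | not stated | subject still in study |

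**4. Is the split ordered by severity?** Not consistently. Safety symptoms and hypersensitivity sit under 9.4.1, while severe AEs that rule out further treatment and related SAEs sit under 9.4.2. A milder case can therefore have less required follow-up than a severe one.

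**5. How many scheduled panels are at risk?** Post-dose panels are Day 1 (2 h), Day 2, Day 5 (2 h), Day 6, FU-V1 and FU-V2, which makes 6. Let the last dose be on Day d, so FU-V1 is Day d + 3 and FU-V2 is Day d + 30. Two assumptions are mine: the subject completes the Day 2 panel, and the Day 5 and Day 6 panels are not done without a Day 5 dose.
- d = 1 to 4: the 9.4.2 route gives 2 + 2 = 4 and the 9.4.1 route requires 2. At risk: 4 − 2 = 2.
- d = 5, exit after Day 6 and before FU-V1: 4 + 2 = 6 against 4. At risk: 6 − 4 = 2.
- Exit between FU-V1 and FU-V2: 1 at risk.

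So up to two scheduled panels per affected subject. An attempted exit panel may add one measurement, but after a Day 1 stop it may be the Day 2 panel itself. An off-schedule panel may also appear only in listings, because SAP 5.4 keeps unscheduled assessments out of summary tables.

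**6. Would an exit panel stand in for the visits?** Example with an assumed exit: last dose Day 2, exit Day 3. FU-V1 is Day 2 + 3 = 5 and FU-V2 is Day 2 + 30 = 32. An exit panel on Day 3 comes 5 − 3 = 2 days before FU-V1 and 32 − 3 = 29 days before FU-V2.

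**7. What could go unseen?** Symptoms reach the AE record by either route. A new laboratory or QTcF change without symptoms is found only if blood is drawn or an ECG is recorded.

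**The case against.** The strongest reply is that 9.4.2 already supplies a default. Its follow-up sentence is general, and a subject whose IMP is stopped for medication fits it as written. Both lists are only potential reasons, and 10.6.1 allows needed medication without any withdrawal. This stands to the extent that the kept-in-study reading is available and sensible. It does not settle the matter, because nothing makes 9.4.2 override 9.4.1, and 10.6.1 names study withdrawal.

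Several safeguards also limit the harm:
- AE monitoring runs to 30 days after the last dose (11.4.2, 12.2). AEs ongoing at withdrawal are followed until resolved or stable (12.2), and clinically relevant vital-sign deviations must be re-measured (11.4.4). These safeguards stand, but they act on findings already known.
- The sentinel review follows completion of FU-V1, and the DSMB review waits for FU-V1 data from all subjects (8.1). A gap would be noticed. Section 8.1 does not say what happens if a withdrawn subject has no FU-V1, and noticing the gap does not recover an ECG that was never recorded.
- A subject may be replaced, although 13.2 limits this to withdrawal for reasons other than safety. Replacement restores the group's size, not the first subject's data.
- Protocol 6.2.2 reports a half-life below 6 hours for earlier oral ciclopirox. At 24 hours after a dose, more than 24 / 6 = 4 such half-lives have passed, so residual exposure is probably small. ATL-001 is a new formulation and may differ.

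Together these points reduce the weight of the concern without removing the conflict.

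**Conclusion.** The concern holds as a permitted gap. Two sections give overlapping routes for one trigger, and one route does not require FU-V1 and FU-V2. The size is up to two scheduled panels per affected dosed subject, and the exposure is mainly a new asymptomatic laboratory or QTcF change after exit. The sponsor should correct the text, but the primary AE analysis is not in doubt.

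A reader might infer more than the documents support:
- *That such subjects must lose follow-up.* Neither list is mandatory, and 9.4.2 offers a route that keeps the visits.
- *That their AE data are lost.* 9.4.1 and Section 12 keep AE follow-up, every dosed subject stays in the Safety set, and a dose-limiting event recorded before exit still counts.
- *That escalation would proceed unaware of the gap.* FU-V1 data are the planned condition for both reviews.
- *That a fixed share of panels, or a number of subjects, would be lost.* The documents give no withdrawal rate. The share depends on the day of the last dose and on whether discharge procedures amount to a full panel, so no percentage is claimed.

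The conclusion rests on reading discharge procedures as not including FU-V1 and FU-V2. The schedule supports this: it uses the discharge label for Day 2 and Day 6 and lists the follow-up visits separately.

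**What to change.** 1. Move three reasons from 9.4.1 to 9.4.2: prohibited medication, safety signs or symptoms, and hypersensitivity.
2. Add to 9.4: *Any subject who has received IMP and is withdrawn by the Investigator or Sponsor should be asked to attend FU-V1 and FU-V2, 3 and 30 days after the last dose taken, unless the subject declines, withdraws consent or is lost to follow-up; these data are included in the analyses.* This also covers decisions made under 10.7 and 14.11, and it respects a subject's choice to leave.
3. In 10.6.1, refer to withdrawal from study treatment instead of from the study, and state that medication taken after the last dose does not lead to withdrawal from follow-up.

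Moving the reasons is needed. If 10.6.1 alone were changed, it would openly contradict the medication reason still listed in 9.4.1.

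The cost is a short text amendment and at most two already planned visits per affected subject. No new visit type is needed, because both visits are already timed from the last dose.

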9.4.2 Withdrawal from Treatment

Subjects may voluntarily discontinue treatment with the IMP for any reason at any time. Subjects may be also withdrawn from the IMP at any time, if deemed necessary by the Investigator.

Potential reasons for withdrawal of subjects from the study treatment are:

 Occurrence of an AE of severe intensity (grade ≥3) which does not justify the continuation of the study treatment, or a SAE that will be judged by the Investigator as at least possibly drug-related

Date: 13 December 2023

Sponsor: Atlas Molecular Pharma S.L. Study Code: ATL001-PI-CEP

NCT No.: 05647343

- Use of non-permitted concomitant medications (see Section 10.6.2)
- The decision of a subject to withdraw from the treatment
- Discontinuation of contraceptives during the treatment period
- Pregnancy

Subjects who discontinue treatment with the IMP should not be considered withdrawn from the study. They should return for follow-up visits. If subjects fail to return for these assessments for unknown reasons, every effort (e.g., telephone, e-mail, and letter) should be made by the Investigator to contact them.

In case of a subject discontinuing the study treatment, he/she may be replaced with another subject, at the Sponsor's discretion. The replacement subject will be assigned to the same regimen dosage.

9.4.3 Lost to Follow-up

A subject will be considered lost to follow-up if he/she repeatedly fails to return for scheduled visits and is unable to be contacted by the study site.

The following actions must be taken if a subject fails to return to the site for a required study visit:

- The site must attempt to contact the subject and reschedule the missed visit as soon as possible and counsel the subject on the importance of maintaining the assigned visit schedule and ascertain whether or not the subject wishes to and/or should continue in the study.
- Before a subject is deemed lost to follow-up, the investigator or designee must make every effort to regain contact with the subject (where possible, 3 telephone calls and, if necessary, a certified letter to the subject's last known mailing address or local equivalent methods). These contact attempts should be documented in the subject's medical record.
- Should the subject continue to be unreachable, he/she will be considered to have withdrawn from the study with a primary reason of lost to follow-up.

Premature Termination of the Study

The Investigator or the Sponsor may terminate this study prematurely for any reasonable cause. The IRB and Ras should be informed promptly.

Conditions that may warrant termination include, but are not limited to:

- The discovery of an unexpected, significant, or unacceptable risk to the subjects enrolled in the study, or potential study subjects
- A decision on the part of the Sponsor to suspend or discontinue development of the IMP

If the RA obtains information that raises doubts about the safety or scientific validity of the clinical study, the RA can suspend or prohibit the study.

If the study is prematurely terminated or suspended for any reason, the Investigator/institution should promptly inform the study subjects and should assure appropriate therapy and follow-up for the subjects.

Version: 4.0 Stu Date: 13 December 2023 NC

Sponsor: Atlas Molecular Pharma S.L. Study Code: ATL001-PI-CEP

NCT No.: 05647343

